6.2.11 Visit 10 - 12 Months Post Visit 2 Follow Up

- Perform focused pulmonary assessment including Vital Signs (heart rate, blood pressure, temperature, respiratory rate, SpO₂) and breath sounds.
- Perform pregnancy test for females of child-bearing potential prior to radiographic procedures.
- Perform post-bronchodilator spirometry.
- Perform Lung Volumes and DLCO
- Perform 6MWT
- Administer SGRQ
- Administer mMRC

- Review medications and O₂ use.
- Record AEs since last follow-up (See Section 7).
- Discuss maintenance rehabilitation activity plan with Subject.
- Take Chest CT

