1.3 Analysis Populations

1.3.1 Intent-to-Treat Population

The Intent-to-Treat (ITT) population will include patients who enrolled in the CROSSOVER study, regardless of whether or not treatment was attempted.

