2. ANALYSIS CONSIDERATIONS

2.1 Subject Disposition

The number of subjects screened, enrolled and treated in the study will be presented. Additionally, the number and percentage of subjects who complete the study to 12 months, 24 months, 36 months, 48 months and 60 months, and who terminate the study prematurely (by visit), will be presented including reasons for premature termination.

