2.2 Demographic and Baseline Characteristics

Demographic and baseline characteristics will be summarized. Baseline is defined as the last assessment evaluated prior to treatment. Demographic and baseline characteristics will be presented with summary statistics (sample size (N), mean, standard deviation (SD), median, minimum, and maximum) for continuous variables and frequency distributions for categorical variables.

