2.3 Endpoint Analyses

2.3.1 Effectiveness Endpoint Analyses

Summary statistics will be provided for change in 6MWT, percent change in FEV1 (L), absolute change in SGRQ (total and individual domain scores), absolute change in RV (L), absolute change in VC and absolute change in RV/TLC from baseline to the 12 month follow-up visit.

Additionally, summary statistics will be provided for the change at each follow-up visit (24 months, 36 months, 48 months and 60 months).

Frequency distributions will be presented for the 6MWT, SGRQ, FEV1 and RV responder rates for each follow-up time period (12 months, 24 months, 36 months, 48 months and 60 months).

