2.7 Additional Descriptive Analysis

Additional descriptive summary statistics will be presented for clinical assessments (such as plethysmography and spirometry measures), procedural and device data, and efficacy results.

For continuous variables, summary statistics (sample size (N), mean, standard deviation (STD), median, minimum, and maximum).

For categorical variables, results will be summarized with frequency distributions by follow-up time period.

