E. Date imputations are applied to the process of assigning treatment period and study day and should be retained in the derived database, but the data listings should display the original, partially missing dates.

F. Specifications regarding the inclusion of AE/CM/PD records

- 1) up to 12-month visit are defined as follows:
 - Completed 12 month visit – then include all records with AE/CM/PD onset dates \leq the actual 12 month visit date.
 - Missing 12 month visit – then include all records with AE/CM/PD onset dates \leq 13 months post treatment #1 date.
- 2) 12 – 24 month are defined as follows:
 - Completed 24 month visit – then include all records with AE/CM/PD onset dates \leq the actual 24 month visit date and \geq actual 12 month visit date.
 - Missing 24 month visit – then include all records with AE/CM/PD onset dates \leq 25 months post treatment #1 date and \geq actual 12 month visit date.
- 3) 24 – 36 month are defined as follows:
 - Completed 36 month visit – then include all records with AE/CM/PD onset dates \leq the actual 36 month visit date and \geq actual 24 month visit date.
 - Missing 36 month visit – then include all records with AE/CM/PD onset dates \leq 37 months post treatment #1 date and \geq actual 24 month visit date.
- 4) 36 – 48 month are defined as follows:
 - Completed 48 month visit – then include all records with AE/CM/PD onset dates \leq the actual 48 month visit date and \geq actual 36 month visit date.
 - Missing 48 month visit – then include all records with AE/CM/PD onset dates \leq 49 months post treatment #1 date and \geq actual 36 month visit date.
- 5) 48 – 60 month are defined as follows:
 - Completed 60 month visit – then include all records with AE/CM/PD onset dates \leq the actual 60 month visit date and \geq actual 48 month visit date.
 - Missing 60 month visit – then include all records with AE/CM/PD onset dates \leq 61 months post treatment #1 date and \geq actual 48 month visit date.

G. Unless otherwise noted, the mean (standard deviation) of a set of values should be printed out to one (two) more decimal(s) than the raw value.

e.g., raw: xx
 mean and standard deviation: xx.x and xx.xx
 range (minimum and maximum): xx, xx

- H. All table percentages should be reported with one decimal point unless otherwise noted.

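### Do the 12–60 month responder rates need a stated denominator and a rule for missing outcomes?

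*SAP*

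**What the plan says.** SAP 1.2.1 sets the responder thresholds: 25 m on the 6MWT, 4 points on the SGRQ, 10% on FEV1 and 0.35 L on RV. SAP 2.3.1 then states: "Frequency distributions will be presented for the 6MWT, SGRQ, FEV1 and RV responder rates for each follow-up time period", and lists 12, 24, 36, 48 and 60 months. The same section plans summary statistics for the change in each of these measures at the same five time points.

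The ITT population in SAP 1.3.1 consists of "patients who enrolled in the CROSSOVER study, regardless of whether or not treatment was attempted". No treated set is defined. SAP 2.2 says "Baseline is defined as the last assessment evaluated prior to treatment". The protocol times follow-up from the first coil placement; Visit 10, for example, is headed "12 Months Post Visit 2 Follow Up".

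On presentation, SAP 2.7 includes the sample size among the statistics for continuous variables. For the rest it says "For categorical variables, results will be summarized with frequency distributions by follow-up time period". SAP 2.1 says "The number of subjects screened, enrolled and treated in the study will be presented". It adds the numbers completing to each of the five time points and the premature terminations by visit, with reasons. SAP 1.4 states that there is no hypothesis or power calculation and that results are descriptive.

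**The concern.** A rate needs a denominator, and none is written down. Read literally, ITT would put never-treated subjects into the denominator. They have no first-placement date from which to count 12 months, and on the wording of SAP 2.2 they have no baseline either.

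The SAP plainly expects missed visits. Appendix 4.1 item F has an entry such as "Missing 24 month visit" for each of the five time points, but only to decide which adverse event, medication and deviation records to include. Item H, "All table percentages should be reported with one decimal point unless otherwise noted", settles the format of a percentage and not its base. SAP 2.7 names N for continuous variables only.

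Two programmers could therefore produce different percentages from the same data. A flat rate from 24 to 60 months could reflect lasting benefit, or it could reflect the loss of subjects who did badly. With no comparator, a reader might take such a rate at face value.

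**Working it through.** There is no planned figure to reproduce: the documents give no sample size, expected response or attrition. The check is whether the planned tables leave the rate undetermined, and how far it could move.

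**1. Is a rule given anywhere?** No. SAP 1.2.1 gives thresholds. Appendix 4.1 items C and D impute adverse event and medication dates, F sets windows for records, H sets decimals and I governs listings. None concerns effectiveness outcomes. Since nothing is imputed for these outcomes, the natural reading is observed cases.

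**2. Is the number assessed shown for each test?** Yes. SAP 2.3.1 requires change summaries for 6MWT, SGRQ, FEV1 and RV at every 12–60 month visit, and SAP 2.7 includes N among the statistics for continuous variables. Each responder definition is a cut-off on that same change. A subject with a change value can be classified, and a subject without one cannot. The N in the change table is therefore the observed-case denominator for each test.

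**3. Can a stricter rate be recovered?** Yes. Let r be the responders (a category count in the frequency table), N the number assessed and T the number treated (SAP 2.1). The observed-case rate is r/N. With every treated subject in the denominator it is r/T. Completers and terminations by visit, with reasons, help to explain T − N.

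**4. Never-treated subjects.** Under the protocol (Synopsis, section 4.6 and the Table 6 footnote), baseline is Visit 1, or the RENEW 12-month values if these are no more than 6 weeks old. It does not depend on later treatment. What these subjects lack is a first-placement date, so they have no 12–60 month change and fall outside N. SAP 2.1 shows enrolled and treated separately. If 5–10% of those enrolled were never treated (assumption), a 50% rate among the treated becomes 0.50 × 0.95 = 47.5% or 0.50 × 0.90 = 45.0% of those enrolled, a fall of 2.5 to 5.0 points.

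**5. Subjects not yet due.** SAP 2.5 places the 12-month analysis after that visit is complete for all patients. Subjects still waiting for the visit should not blur the 12-month rate.

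**6. Size of the choice left open.** Protocol Tables 1–4 give numbers tested at 6 and 12 months in the earlier studies outside the US. If a share s of those due is tested and a share p of those tested responds, counting the untested as non-responders gives p × s.

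| Test | Tested at 12 / 6 months | s | p × s at p = 0.50 | Gap (points) |
|---|---|---|---|---|
| 6MWT | 71/110 | 0.645 | 0.323 | 17.7 |
| RV | 74/112 | 0.661 | 0.330 | 17.0 |
| FEV1 | 73/106 | 0.689 | 0.344 | 15.6 |
| SGRQ | 74/111 | 0.667 | 0.333 | 16.7 |

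For 6MWT the gap is 14.2 points at p = 0.40 and 21.3 at p = 0.60. All of these assume that the 12-month subjects are a subset of the 6-month subjects and that everyone else was due. If nobody else was due, the gap is 0.

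A wholly assumed grid (0–10 never treated per 100 enrolled, 50–90% of the treated assessed, 30–60% of those assessed responding) gives gaps between r/N and responders over all enrolled from 30.0 − 27.0 = 3 points to 60.0 − 27.0 = 33 points. These are differences between two rates that a reader can compute, not errors in either.

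**7. Would a second, written rate be cleaner?** Not automatically. Suppose its denominator takes only subjects whose ±4 week window (Protocol Table 6) has closed. With 10 assessed, 5 responders and 2 assessed non-responders whose windows are still open, the observed rate is 5/10 = 50.0% and the second could be 5/8 = 62.5%. A rate meant to be the cautious one would then be the higher.

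**The case for a change.** The strongest case for a change is that, in a single-arm study without a test, the percentages are the effectiveness result, so their base should be fixed beforehand. The authors wrote a missed-visit rule for safety records at all five time points and none for effectiveness. Disposition counts are per subject and cannot stand in for per-test counts: in the earlier studies the numbers tested at one visit ran from 106 to 112 at 6 months and from 71 to 74 at 12. SAP 2.5 does not repeat the all-patients condition for the 24–60 month analyses, and Protocol 8.1 allows early closure, so subjects lost and subjects not yet due could be mixed later on.

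Part of this stands. The rule is absent, and a sentence calling the rates observed-case would do no harm. From 24 months on, separating lost from not due depends on the termination reasons in SAP 2.1. But the per-test argument is answered by the change summaries, which carry N for each test at each visit. Early closure is a contingency, and subjects stopped by it would appear among the premature terminations. Counting missing outcomes as non-response is one convention among several, and it understates response when visits are missed for unrelated reasons.

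**Conclusion.** No change is needed. This is missing detail that analysts would fill in the usual way, with responders over subjects assessed. No stated rule leads to a wrong result, and no error rate, sample size or decision depends on the choice.

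The two denominators could differ by 0 to 17.7 points in the 6MWT illustration at 50% response. That range does not measure attrition in this study. It comes from pooled counts at a 31 May 2013 cut, with no cause given for the fall in N, and says nothing about 24–60 months. Never-treated subjects are the smaller part, at 2.5 to 5.0 points on an assumed 5–10%, and the documents do not show that there are any.

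The conclusion rests on two assumptions: that the change summaries show N at each visit as SAP 2.7 lists, and that the frequency tables show counts as well as percentages. If both hold, a reader sees how many subjects lie behind each rate and can compute the stricter one.

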2.3.2 Safety Endpoint Analyses

Treatment emergent adverse events (AEs), serious adverse events (SAEs) and major complications will be summarized. AE and major complication summaries will include all events experienced within the first 12 month visit and each follow-up time period. Overall summaries will be presented, but shorter periods of time prior to 12 month visit will be considered as well. In order to assess the safety profile of the LVRC without the interference of the procedure effect, the timing of adverse events and major complications with respect to the treatment visits will be considered.

2.3.2.1 Event Time Periods

In order to assess the safety profile of the LVRC without the interference of the procedure effect, adverse events and major complications will be summarized by time period. Each event will be included in the time period in which the event began, with the periods defined as follows:

- Peri-procedural: 0-30 days post each of the two treatment visits (visit 2 or visit 5)
- Between treatment #1 and visit 5: More than 30 days after visit 2, but prior to visit 5
- Between treatment #2 (or treatment #1 for subjects that miss Visit 5) and 6 months: More than 30 days after visit 5, but prior to 6 months post treatment #1

- Between 6 and 12 months: 6 or more months post treatment #1 through visit 10

Regarding the programming specifications for inclusion of AE records through the 12-month visit and each follow-up time period, please refer to Appendix 4.1 (item F).

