2.3.2.3 Adverse Events

MedDRA system organ classes and preferred terms will be summarized for all AEs. Summaries will include event and subject counts. For the events summarized by subject counts, each subject will be counted only once within a system organ class or a preferred term by using the adverse events with the highest severity within each category.

SAE, AEs, and AEs related to device or procedure will be summarized separately. Additionally, summaries for major complications will also be included. A high level summary for SAEs and AEs will also be provided. All summaries will be presented by each follow up time period. Similarly, device or procedure related SAEs and non-SAEs will be presented by severity.

In addition, all information pertaining to AEs noted during the study will also be listed by subject. Details of the line listing by subject will include verbatim term given by the Investigator, preferred term, system organ class, start date, stop date, severity, and device or procedure relatedness. The AE onset will also be shown relative (in number of days) to the day of the procedure.

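### First-year safety tables give counts over periods of about 30 to 183 days with no numbers at risk or person-time, so the counts cannot be read against each other as risk

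*SAP*

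**What the plan says.** The purpose of the split is given in SAP 2.3.2 and again in 2.3.2.1: "In order to assess the safety profile of the LVRC without the interference of the procedure effect". To that end SAP 2.3.2.1 says that "adverse events and major complications will be summarized by time period", and it places each event in the period in which it began. There are four first-year periods:

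- Peri-procedural: days 0 to 30 after each of the two placements.
- Treatment #1 to Visit 5: "More than 30 days after visit 2, but prior to visit 5".
- Treatment #2 to 6 months: "More than 30 days after visit 5, but prior to 6 months post treatment #1". For subjects who miss Visit 5 this period is counted from treatment #1.
- "Between 6 and 12 months: 6 or more months post treatment #1 through visit 10".

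For the measure, SAP 2.3.2.3 says: "Summaries will include event and subject counts". SAP 1.2.2 likewise tabulates subjects with at least one major complication within 12 months and within blocks of time. Appendix 4.1 F says which records fall in the first year and in each later year. Neither document specifies person-time, an exposure-adjusted rate, a time-to-event summary or a number at risk per period.

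**The concern.** A count depends on both the risk and the time observed. When one period is several times longer than another, the longer one collects more events even if nothing about the risk has changed. Anyone using these tables to judge how the device performs away from the procedure will look from the peri-procedural column to the later columns, and without exposure that step can mislead in either direction. A flat hazard looks like accumulating late harm, and a real early excess looks like no excess.

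Exposure also differs between subjects in ways that fixed period lengths do not capture: a missed Visit 5, a late or early Visit 5, death, withdrawal, and subjects enrolled but never treated. The only analysis population the SAP defines (1.3.1) is ITT, which includes subjects in whom placement was never tried. If ITT is the denominator for the period tables, such subjects count in periods they never entered.

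**Working it through.** The plan gives no event rate or comparison figure for these tables, so there is nothing of its own to reproduce. The check derives period lengths from the SAP and then shows what they do to counts.

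**Inputs**
- Period definitions: SAP 2.3.2.1.
- Visit 5 about 2 months after Visit 2: Protocol 4.6.1. Protocol Table 6 gives it no visit window.
- Visit 10 window of ±4 weeks: Protocol Table 6.
- Cut-off at 13 months if the 12-month visit is missing: SAP Appendix 4.1 F.
- One month = 365.25/12 = 30.44 days (convention).
- Event rates of 0.5, 1 and 2 per person-year, constant, with full follow-up (assumptions, for illustration only).

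**Period lengths**
- Peri-procedural: 31 days per placement; 2 × 31 = 62 days for both.
- Treatment #1 to Visit 5: 60.9 − 31 = 29.9 days.
- Treatment #2 to 6 months: 182.6 − (60.9 + 31) = about 90.8 days.
- 6 to 12 months: 365.25 − 182.6 = 182.6 days.
- Sum: 62 + 29.9 + 90.8 + 182.6 = about 365.25 days, so the year is fully covered.

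**Constant hazard, no true difference between periods**

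Events per 100 subjects = 100 × rate × days / 365.25. Proportion with at least one event = 1 − exp(−rate × days / 365.25).

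| Period | Days | Events per 100 at rate 0.5 / 1 / 2 | Subjects with ≥1 event at rate 1 |
|---|---|---|---|
| Peri-procedural (both) | 62 | 8.5 / 17.0 / 33.9 | 15.6% |
| Treatment #1 to Visit 5 | 29.9 | 4.1 / 8.2 / 16.4 | 7.9% |
| Treatment #2 to 6 months | 90.8 | 12.4 / 24.8 / 49.7 | 22.0% |
| 6 to 12 months | 182.6 | 25.0 / 50.0 / 100.0 | 39.3% |

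The contrast that bears on the SAP's purpose is 6-12 months against peri-procedural:
- Event counts: 182.6 / 62 = 2.9, whatever the rate. Against a single 31-day window it is 182.6 / 31 = 5.9.
- Subject counts: 39.3 / 15.6 = 2.5 at rate 1. At rate 0.5 it is 22.1 / 8.1 = 2.7, and at rate 2 it is 63.2 / 28.8 = 2.2.

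**The reverse case**

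Suppose each period shows 20 events per 100 fully followed subjects. The rates are 20 / (100 × days / 365.25) = 1.18, 2.45, 0.80 and 0.40 per person-year, in table order. Dividing by 12 and multiplying by 100 gives 9.8, 20.4, 6.7 and 3.3 per 100 patient-months. The peri-procedural and 6-12 month counts are equal, while the rates differ by 1.18 / 0.40 = about 2.9.

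**Why nominal lengths do not settle it**
- Visit 5 missed: one window of 31 days, then 182.6 − 31 = 151.6 days to 6 months. The later-to-peri-procedural exposure ratio is 151.6 / 31 = 4.9, against 90.8 / 62 = 1.5 for a subject with both placements.
- Visit 5 at day 45 or day 90 (assumed range): treatment #1 to Visit 5 lasts 14 or 59 days, and treatment #2 to 6 months lasts about 107 or 62 days.
- Visit 10 window: 6-12 months lasts 182.6 ± 28 = about 155 to 211 days, or up to about 213 days if Visit 10 is missing. The ratio to 62 days is then 2.5 to 3.4.

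**The case against.** The SAP says events are summarized by period. It plans no contrast or test between periods, and SAP 1.4 restricts the study to descriptive results. Its stated aim can be read as setting peri-procedural events aside so that later ones are seen alone, and assigning events by onset does that. The plan also lists each event's onset day relative to the procedure, tabulates device- or procedure-related events separately, reports terminations by visit (SAP 2.1), and has a rule for subjects who miss Visit 5. A reader could scale counts by nominal period length.

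Much of this stands. A reader might infer that the SAP plans a formal comparison across periods; it does not. A reader might also infer that the tables cannot show anything about device safety apart from the procedure. That goes too far, because later-period counts are a partial view of events away from placement. Nor should the roughly six-fold spread between the longest and shortest periods (182.6 / 29.9 = 6.1) be taken as the size of the problem: neither of those periods is peri-procedural. The unequal-length argument does not extend to the annual periods, which are each nominally one year, so there only attrition matters.

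The rest does not answer the point. A rate is itself a descriptive statistic. The onset-day listing has no denominator. Terminations by visit do not give days at risk within these periods. The relatedness tables merge device and procedure, and the relatedness definitions in Protocol 7.4 refer only to the procedure, so the time split is the plan's main way of telling the two apart. Nominal scaling fails where exposure differs by subject.

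**Conclusion.** The concern holds as a missing exposure denominator. The tables remain usable for showing which events began near a procedure and which later, but the counts should not be read against each other as risk. On nominal lengths, equal event counts in the peri-procedural and 6-12 month periods would correspond to a peri-procedural rate about 2.9 times the later one (about 2.5 to 3.4 across the Visit 10 window). A near three-fold procedure effect could therefore look like none.

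The size rests on Visit 5 at 2 months, both placements done, full follow-up and a constant hazard within each period. The event-count ratio does not depend on the assumed rate; the counts and percentages do. The documents supply no event rate, so nothing here predicts what the study will show. This should be corrected before the tables are produced, but it does not call the design or the data into question.

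**What to change.** In SAP 2.3.2.1, for each first-year period table, add:

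- the number of treated subjects at risk entering the period;
- total days at risk, truncated at death, study exit or the next procedure;
- events per 100 patient-months.

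Show the peri-procedural window separately for each placement, so that subjects with one placement are handled properly. State that any reading of peri-procedural against later periods rests on the rates. If confidence intervals are given, use a method that allows for repeat events within a subject, or restrict them to first events. For the annual periods from 12-24 to 48-60 months, add numbers at risk and person-time to account for attrition.

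The cost is a few derived variables and table columns. The treatment, visit, onset and exit dates are already needed for the planned disposition and period assignments, so no new data are required. One limitation remains: a rate averages over risk that may change within a period, particularly in the first 30 days. The onset-day listing should therefore stay alongside it.

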With respect to safety, the Coil has been designed to be as safe as possible, which is supported by the fact that the Serious Adverse Event profile of the device is comparable to that reported in the literature for bronchoscopy alone in a sham procedure, specifically, referenced in the control patient population in the EASE trial (Shah, 2011), which observed 107 individuals for 6 months. Comparing the PneumRx OUS study results to the EASE sham control group, it appears that the risks associated with the Coil System are largely attributable to the bronchoscopic procedure itself rather than to the device per se. Specifically, the rate of serious events of pneumothorax, hemoptysis, COPD exacerbation and pneumonia are comparable between the LVRC treatment population and the EASE sham control group.

Table 5. Comparison of 6-Month SAE Data Per Procedure - LVRC System vs. EASE Sham Control

Reported SAE	PneumRx OUS studies (up to 6 Months)	EASE sham control (6 Months reported data)
Pneumothorax	14/238 procedures = 5.9%	1/107 procedures = 0.9%
Hemoptysis	1/238 procedures = 0.4%	0/107 procedures = 0%
Respiratory Failure	0/238 procedures = 0%	0/107 procedures = 0%
COPD exacerbation/ pneumonia ¹	41/238 procedures = 17.2%	18/107 procedures = 16.8%
Death	1*/238 procedures = 0.4%	4/107 procedures = 3.7%

* Not related to device or procedure

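### The SAP pools the 30 days after the first and second Coil procedures into one peri-procedural period, and no planned summary gives early risk by procedure

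*SAP*

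**What the plan says.** SAP 2.3.2.1 allocates adverse events and major complications to periods by onset date: "Each event will be included in the time period in which the event began, with the periods defined as follows". Four periods run up to Visit 10. The first covers both procedures: "Peri-procedural: 0-30 days post each of the two treatment visits (visit 2 or visit 5"). The next begins only after day 30: "Between treatment #1 and visit 5: More than 30 days after visit 2, but prior to visit 5". The third allows for subjects with one procedure: "Between treatment #2 (or treatment #1 for subjects that miss Visit 5) and 6 months". The stated aim is "In order to assess the safety profile of the LVRC without the interference of the procedure effect", and SAP 2.3.2 adds that "the timing of adverse events and major complications with respect to the treatment visits will be considered".

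SAP 2.3.2.3 plans both event counts and subject counts. In the subject counts "each subject will be counted only once within a system organ class or a preferred term". It also plans a by-subject listing with start date, severity, relatedness and onset in days from the procedure, in the singular. SAP 1.3.1 defines one population, ITT, which includes enrolled subjects whether or not treatment was attempted. SAP 2.4 lists subgroups by region, heterogeneity and air trapping, and none by procedure or lung.

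Protocol 4.6.1 plans two procedures, the second in the other lung about 2 months after the first. Protocol 2.4, Table 5, reports earlier serious events per procedure, for example pneumothorax "14/238 procedures = 5.9" per cent.

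**The concern.** SAP 1.4 makes the study descriptive, and SAP 1.2.2 builds the primary safety analysis on tabulating subjects with major complications within 12 months and within blocks of time. How those blocks are drawn therefore decides what the safety tables can show. The protocol itself attributes most Coil risk to the bronchoscopic procedure, so the 30 days after each procedure are the windows of most interest.

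With both windows in one category, a reader of the tables cannot see the early risk after procedure #1 or after procedure #2. Nor can the pooled percentage be interpreted without knowing how many subjects had two procedures, one or none, because that mix moves the percentage even when the risk of each procedure is constant.

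**Working it through.** The documents give no event rate or sample size for this point, so there is no plan figure to reproduce. The check has two parts.

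**Reading the text.** The allocation rule has one peri-procedural category. No table, subgroup or denominator in the SAP separates Visit 2 from Visit 5. SAP 2.3.2.1 names no denominator for the period, so ITT applies by default; that is an inference from its being the only population defined. Subjects with no procedure, one procedure and two procedures would then share the denominator. The listing could separate the procedures, but it does not say which one its relative day refers to. Appendix 4.1, item C, has the same gap: some partial start dates are set to the treatment date without naming the treatment.

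**Illustration.** Inputs, all assumed except the anchor:
- p1, p2: 30-day risks after procedures #1 and #2, centred on 14/238 = 5.9% (Protocol Table 5). That is a rate up to 6 months and is borrowed here only for scale.
- q: share of treated subjects who have procedure #2. It is not given, so 1.0, 0.9 and 0.8 are shown.
- Events after the two procedures are independent.

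Formulas:
- Pooled risk per subject = q × [1 − (1 − p1)(1 − p2)] + (1 − q) × p1
- Pooled risk per procedure = (p1 + q × p2) / (1 + q)

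Worked case, p1 = p2 = 0.059: with q = 1, 1 − 0.941² = 0.1145. With q = 0.8, 0.8 × 0.1145 + 0.2 × 0.059 = 0.103.

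| p1, p2 | q = 1.0: subject / procedure | q = 0.9 | q = 0.8 |
|---|---|---|---|
| 5.9%, 5.9% | 11.5% / 5.9% | 10.9% / 5.9% | 10.3% / 5.9% |
| 3.0%, 8.8% | 11.5% / 5.9% | 10.7% / 5.7% | 9.8% / 5.6% |
| 8.8%, 3.0% | 11.5% / 5.9% | 11.3% / 6.1% | 11.0% / 6.2% |

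Down the first results column, equal risks and a roughly threefold difference in either direction give the same pooled figures. Across the first row, the per-subject figure falls by about one point with no change in risk, while the per-procedure figure stays at 5.9%. For a commoner event, 41/238 = 17.2% (COPD exacerbation or pneumonia), the same fall in q moves the per-subject figure from 31.4% to 28.6%. If a fraction u of the ITT denominator has no procedure, every per-subject figure is multiplied by (1 − u).

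**Does drop-out because of the event lower the figure?** Suppose every subject with the event after procedure #1 misses procedure #2. The pooled risk is 0.059 + 0.941 × 0.059 = 0.1145, the same 11.5% as with no drop-out, because those subjects are already in the numerator. The fall to 10.3% arises only when procedure #2 is missed for reasons unrelated to the event counted.

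**The case against.** The strongest reply is that the information is not lost and that the periods serve another purpose. Pooling both windows suits the stated aim of setting the procedure effect aside, no objective asks for second-lung risk, and SAP 2.3.2 undertakes to consider timing relative to the treatment visits. This stands in part: no planned figure is wrong and no error rate is affected. But the sentence on timing commits to no table, and the operative definition in 2.3.2.1 merges the windows.

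Several stronger readings are tempting and are not supported:
- *Risk by procedure is never reported.* The by-subject listing gives start dates and relative onset, so events could be assigned by hand if treatment dates are to hand. The SAP numbering also jumps from 2.3.2.1 to 2.3.2.3, which may be only a slip but is a reason to avoid an absolute claim.
- *A subject with the event after both procedures is counted once.* True of the subject counts. The event counts would record both, though without showing which procedure each followed.
- *Drop-out for harm hides that harm.* Not for the event counted, as shown above.
- *Table 5 calls for the split.* It supports a per-procedure unit, but it pools first and second procedures and runs up to 6 months, so it is not a benchmark for 30-day columns.
- *Separate columns would show the excess risk of treating the second lung.* Those who reach procedure #2 have come through procedure #1, so the comparison is between selected groups.

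**Conclusion.** The point holds as a gap in table specification. The SAP specifies no summary of 30-day risk by procedure and no denominator of subjects who had each procedure, and the pooled subject-level percentage mixes different numbers of risk windows.

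On the illustrative rates, the pooled figure cannot distinguish equal risks from a roughly threefold difference in either direction when all subjects have both procedures. It shifts by about one percentage point (11.5% to 10.3%) when a fifth have only the first. Those sizes rest on assumed risks, independence, an assumed share with the second procedure, and a 6-month rate used for scale. Nothing in the documents shows that risk differs between the procedures. That the pooled category cannot show the risk of each procedure does not depend on the rates chosen. What is at stake is the interpretability of a descriptive safety summary; no test or sample size is affected.

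**What to change.** In SAP 2.3.2.1, replace the single category with two for AEs, SAEs and major complications:
- Peri-procedural #1: days 0-30 after Visit 2; denominator, subjects who had treatment #1.
- Peri-procedural #2: days 0-30 after Visit 5; denominator, subjects who had treatment #2.

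Add a row giving procedures with at least one event over all procedures performed, and keep the pooled column. In SAP 2.3.2.3, state which procedure the listing's relative day counts from. The date-imputation rule in Appendix 4.1, item C, needs the same clarification so that partially dated events fall in a defined column. A footnote should say that the two columns are descriptive and concern different, selected groups.

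The cost is some SAP wording and extra table columns, using dates already collected. The drawback is a smaller denominator, and so a less precise percentage, for treatment #2. Nothing in treatment or follow-up changes.
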